6.8.3. Missing Start and Stop Dates for Adverse Events

The same conventions to address incomplete dates for prior and concomitant medications (see Section 6.8.2 above) will also be used for AEs.

7. GENERAL CONSIDERATIONS FOR DATA ANALYSES

Continuous variables (eg, age) are summarized using descriptive statistics (the number of subjects with available data, the mean, standard deviation (SD), median and minimum and maximum). Categorical variables (eg, race) are summarized using counts and percentages.

The following conventions are applied to all data presentations and summaries.

- For continuous variables, all mean and median values are formatted to one more decimal place than the measured value. Standard deviation values are formatted to two more decimal places than the measured value. Minimum and maximum values are presented with the same number of decimal places as the measured value.
- For categorical variables, the number and percentage of responses are presented in the form XX (XX.X%) where the percentage is in the parentheses.
- Date variables are formatted as DDMMMYYYY for presentation. Time is formatted to 24-hour format as HH:MM for presentation, if applicable.
- Wherever possible, data will be decimal aligned.
- Any row with all zeros will not appear except with reasons for not completing the study. Summary tables will clearly indicate the number of subjects to which the data apply. If a table, listing, or figure has no available data, then the body should read 'No data to report.'

7.1. Treatment group Descriptors

There were only 3 screened subjects who had historical C3G in this study. Two of them had confirmed C3G per central pathologist and started BCX9930 under 500 mg BID. The unconfirmed C3G subject was a screen failure. No subjects were enrolled under the other two cohorts (IgAN and PMN).

Disposition summaries will be presented by the 'C3G' cohort and all screened subjects.

Demographics and baseline characteristics summaries will be presented by the 'C3G' cohort. All other summaries will be presented by the following dosing groups:

- C3G 500 mg BID
- C3G 500 mg Total Daily Dose
- Total All Doses (Efficacy summaries will not have this column).

8. DATA DISPLAYS RELATED TO THE STUDY POPULATION

8.1. Subjects Disposition

Subject disposition will be summarized by C3G cohort and all screened subjects. The number of subjects who screened, had historical C3G, had confirmed C3G and among them, the number and percentage who were screening failures (along with the reasons) will be summarized. The number of subjects in safety population (treated), and among them, the number and percentage of subjects who discontinued from the study (along with the reasons) and those who completed the study will be presented. These data will also be listed.

A consort diagram will also be provided to display a graphical view of the study status.

8.2. Screen Failures

Screening failure information will be summarized in the subject disposition table (see Section 8.1 above) and listed.

8.3. Protocol Deviations

Protocol deviations will be identified by major or minor status, category, and importance per the protocol deviations plan. Protocol deviations will be listed.

8.4. Demographic and Baseline Characteristics

Demographic data and baseline characteristics including age at time of consent, age category at time of consent (< 18, 18-64, ≥ 65 with subcategories 65-74 and ≥ 75), sex at birth, childbearing potential (females only), ethnicity, race, height, weight, and BMI will be summarized by the C3G cohort.

Demographic data and baseline characteristics data will be listed.

8.5. Listing of Subject Inclusion and Exclusion Criteria

Inclusion/exclusion criterion not met will be listed.

8.6. Medical History and Medical Conditions Present at Entry

Medical history, including disease specific medical history, will be coded using the Medical Dictionary for Regulatory Affairs (MedDRA) version 24 and listed.

8.7. Prior Medication History and Medications Present at Entry

Any medication that was received and stopped prior to the date of first dose will be considered prior medications. Prior medications will be listed.

8.8. Baseline Physical Examination

Baseline physical examination data will be listed.

8.9. Baseline Vital Signs

Baseline vital sign data will be listed.

8.10. Baseline Laboratory Data

Baseline laboratory data will be listed.

8.11. Baseline Primary and Secondary Efficacy Evaluations

See Section 9.

9. EFFICACY

Due to the study discontinuation at a total of 2 treated subjects, efficacy analysis will be limited to descriptive statistics for the following key efficacy endpoints: 24-hour uPCR, 24-hour urine protein excretion and eGFR.

Descriptive statistics will be presented on observed values, change from baseline, percent change form baseline and ratio to baseline by scheduled visit using nominal visits. Source data of these key efficacy endpoints will be listed.

Source data collected for all other efficacy endpoints will be listed.

9.1. General Considerations

Not applicable.

9.2. Testing Statistical Assumptions Including Comparability at Baseline

Not applicable.

9.3. Statement of the Null and Alternate Hypotheses

Not applicable.

9.4. Subgroup Analyses

Not applicable.

9.5. Multiple Comparisons and Multiplicity

Not applicable.

9.6. Analysis of the Primary Efficacy Endpoint

See introduction to Section 9 above.

9.6.1. Primary Efficacy Analysis

See introduction to Section 9 above.

9.6.2. Sensitivity Analyses of the Primary Efficacy Results

Not applicable.

9.7. Analysis of the Secondary Efficacy Endpoints

See introduction to Section 9 above.

9.8. Summary of Reasons for Exclusion from the Per Protocol Efficacy Analyses

Not applicable.

10. SAFETY AND TOLERABILITY

All AEs and SAEs, regardless of investigator attribution, will be collected from the time of signing of the informed consent through to the last study visit (ie, through the post treatment follow-up visit[s]). TEAEs are defined, within a dosing group, as AEs that started on or after the first dose of study treatment through 30 days after the last dose of study drug.

An overall summary of TEAEs will be presented by dosing group for the followings:

- Number and proportion of subjects with a treatment-emergent adverse event (TEAE)
- Number and proportion of subjects with an investigator rated TEAE of mild, moderate, or severe.
- Number and proportion of subjects with a TEAE related to study drug
- Number and proportion of subjects with a TEAE leading to treatment interruption
- Number and proportion of subjects with a TEAE leading to treatment discontinuation
- Number and proportion of subjects with a TEAE leading to study discontinuation
- Number and proportion of subjects who experience a Common Terminology Criteria for Adverse Events (CTCAE) Grade 3 or 4 TEAE
- Number and proportion of subjects who experience a treatment-emergent serious adverse event (TESAE)
- Number and proportion of subjects with a TEAE leading to death

With respect to severity, if a subject has the same event more than once, the event with the highest severity will be counted. Likewise, if a subject has the same event more than once, the event with the highest relationship to investigational product will be counted. If the relationship between the AE or SAE and the study drug is determined to be possibly, probably, or definitely related, the event will be considered related to the study drug. If an adverse event has a missing severity or relationship, it will be classified as having the highest severity and/or strongest relationship to study treatment.

All AEs will be listed.

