Each eligible subject who consents to participate in the study will receive up to 52 weeks of BCX9930. All subjects will be required to attend at least 9 in-clinic study visits through 24 weeks: Day 1 (Baseline), Week 1 (Day 8), Week 2 (Day 15), Week 4 (Day 29), Week 8 (Day 57), Week 12 (Day 85), Week 16 (Day 113), Week 20 (Day 141), and Week 24 (Day 169) and 5 additional safety assessments visits at Weeks 3 (Day 22), Week 5 (Day 36), Week 6 (Day 43), Week 7 (Day 50), and Week 10 (day 71), either at the investigative site, at a local laboratory more convenient for the subject or via a home health service (where permitted and available). At the Week 24 Visit, the clinical benefit of BCX9930 treatment will be assessed by the investigator. Subjects who are assessed as deriving clinical benefit will continue treatment up to Week 52 and be required to attend at least 7 additional in-clinic visits: Week 28 (Day 197), Week 32 (Day 225), Week 36 (Day 253), Week 40 (Day 281), Week 44 (Day 309), Week 48 (Day 337), and Week 52 (Day 365). All subjects will return to the clinic approximately 4 weeks (28 ± 3 days) after the date of their last dose of BCX9930 for the safety FU Visit.

An on-treatment, percutaneous needle biopsy of the kidney will be performed for subjects with C3G at a specified visit after completion of all other assessments, or during the specified times as described in Section 12.4.2. The on-treatment biopsy is optional for the IgAN and PMN cohorts. All subjects who undergo kidney biopsy should remain on study drug at least until the day of biopsy. Digital images and details from the local pathology reports from the on-treatment biopsies will be reviewed by the central pathologist to evaluate and describe changes from the baseline, pre-treatment digital images.

Protocol BCX9930-211

Version 4.0: 04 August 2022

An optional serial PK/PD substudy will include subjects who provide consent from each of the 3 cohorts to evaluate the PK and PD of BCX9930 at the Day 1 Visit and/or at a subsequent visit prior to the Week 24 Visit. Serial sampling of urine and blood will be performed over a period of 6 hours. Subjects who do not participate in the Baseline (Day 1) PK/PD sample collection are eligible to participate at a subsequent clinic visit prior to the Week 24 Visit.

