11.3.6. Safety follow-up Visit

All subjects will return to the clinic approximately 4 weeks (28 ± 3 days) after the date of their last dose of BCX9930 for safety assessments.

The following assessments will be performed:

 Administration of questionnaires. Where possible, the questionnaire should be completed by the subject prior to other assessments (for early discontinued subjects only):

- 12-lead ECG
- Vital signs (blood pressure, temperature, and pulse rate)
- Targeted physical examination (ie, symptom driven, targeted to new signs and symptoms)
- Weight and BMI
- Single void urine collection for urinalysis including microscopy, and biomarkers
- Blood collection for clinical chemistry, hematology, coagulation, and PD biomarkers
- A urine pregnancy test for female subjects of childbearing potential
- Review and capture of concomitant medications and AEs
- Collection of intended 24-hour urine sample with the number of days between last dose and collection documented
- Study drug accountability

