13.1. Definitions

13.1.1. Adverse Event

An AE is any untoward medical occurrence in a clinical study subject. No causal relationship with the study drug/IMP or with the clinical study itself is implied. An AE may be an unfavorable and unintended sign, symptom, syndrome, or illness that develops or worsens during the clinical study. Clinically relevant abnormal results of diagnostic procedures including abnormal laboratory findings (eg, requiring unscheduled diagnostic procedures or treatment measures, or resulting in withdrawal from the study) are considered to be AEs. Abnormal results

of diagnostic procedures that are incidental or not clinically relevant are not reportable as AEs. If the diagnostic procedure prompts no additional treatment, visits, or monitoring, it will not meet the definition of an AE.

This includes the following:

- AEs not previously observed in the subject that emerge during the protocol-specified AE reporting period (see Section 13.4).
- Findings from protocol-mandated interventions. This can include laboratory assessments performed in the course of the clinical study. AEs should be reported only if the abnormalities are changes from baseline and are clinically significant as described above.
- Pre-existing medical conditions (other than the condition being studied) judged by the
 investigator to have worsened in severity or frequency or changed in character during
 the protocol-specified AE reporting period. When recording such events on an
 AE/SAE eCRF page, it is important to convey the concept that the preexisting
 condition has changed by including applicable descriptors (eg, "more frequent
 headaches").

Symptoms or abnormalities related to the underlying disease (C3G, IgAN, and PMN), such as worsening of kidney laboratory parameters, are considered disease progression and are not to be recorded as AEs unless the event is an SAE or related to treatment with BCX9930 or related to some other cause (eg, concomitant treatment/procedure).

Surgical procedures should not be reported as AEs. The condition for which the surgery is required should be reported as the AE if it occurs or is detected during the study period. Planned surgical measures permitted by the clinical study protocol and the conditions(s) leading to these measures are not AEs if the condition(s) was (were) known before the start of study treatment. In the latter case, the condition should be reported as medical history.

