An optional serial PK/PD substudy was to include subjects who provided consent to evaluate the PK and PD of BCX9930 at the Day 1 Visit and/or at a subsequent visit prior to the Week 24 Visit. Serial sampling of urine and blood was to be performed over a period of 6 hours. Subjects who did not participate in the Baseline (Day 1) PK/PD sample collection were eligible to participate at a subsequent clinic visit prior to the Week 24 Visit.

All subjects were to have a single blood sample drawn for PK analysis at each clinic visit ("sparse sampling" to support PPK and PK/PD modeling). For subjects participating in the serial PK/PD substudy, a single blood sample was to be drawn for PK and PD analysis at visits where serial blood samples were not collected through post dose.

All subjects who signed a separate informed consent (optional) were to participate in exploratory pharmacogenomics testing at a single visit from Day 1 up to the Week 24 Visit (including the safety FU Visit, if applicable).

Figure 1: Study Schema by Protocol Version

Protocol Version 3.0

Screening*							500 mg BCX9930 BID ^{‡ ‡}								F			
Weeks	-8		1	2	4	8	12	16	20	.+ 24	28	32	36	40	44	48*	52	54 [∓]
Days	-56	1	8	15	29	57	85	113	141	169	197	225	253	281	309	337	365	-

^{* =} Kidney Biopsies: A screening biopsy may be waived with approval of central pathologist and agreement with the medical monitor for any subject with a prior biopsy ≤ 30 days prior to screening and ≤ 90 days prior to screening for adolescents with C3G.

Subjects with C3G will undergo a percutaneous needle biopsy of the kidney at the Week 24 Visit or within 7 days after the visit. The Week 24 biopsy procedure is optional for adolescent subjects with C3G.

Subjects with IgAN will undergo a percutaneous needle biopsy of the kidney at the Week 36 Visit or within 7 days after the visit.

Subjects with PMN will undergo a percutaneous needle biopsy of the kidney at the Week 48 Visit to within 3 days after the Week 52 Visit. Dosing with BCX9930 will continue until the Week 52 Visit or until the day of the biopsy procedure.

[figure not shown]
+ = Clinical Benefit Assessment

T = Follow-up/End of Treatment Visit: 14 ± 3 days after last dose of BCX9930 for all subjects

= Safety Follow-up Visit: 28 ± 3 days after last dose of BCX9930 for subjects who discontinue BCX9930 dosing prior to the Week 52 Visit
 F= Follow-Up

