10.4. Routine Laboratory Data

An assessment of drug induced liver injury (DILI) for elevations in liver function tests will be performed. For ALT, AST, total bilirubin and international normalized ratio (INR) within a dosing group, the maximum post-baseline value across a subject's visits (scheduled and unscheduled, out to 30 days post dose) will be determined for each test. The maximum value for each parameter will then be summarized per the categories given below:

ALT/ AST/ ALT and AST/ ALT or AST	Total Bilirubin	INR	ALT or AST and Total Bilirubin
> 1.5X ULN > 3X ULN > 5X ULN > 10X ULN > 20X ULN	> ULN > 1.5X ULN > 2X ULN	> 1.5	ALT > 3X ULN and Total Bilirubin > 1.5X ULN ALT > 3X ULN and Total Bilirubin > 2X ULN AST > 3X ULN and Total Bilirubin > 1.5X ULN AST > 3X ULN and Total Bilirubin > 2X ULN (ALT > 3X ULN or AST > 3X ULN) and Total Bilirubin > 1.5X ULN (ALT > 3X ULN or AST > 3X ULN) and Total Bilirubin > 2X ULN (ALT > 3X ULN or AST > 3X ULN) and Total Bilirubin > 2X ULN)

Within a specific outcome (eg, ALT, AST, etc.), the categories are descending cumulative and not mutually exclusive.

In addition, for serum creatinine, within a dosing group, the maximum post-baseline value across a subject's visits (scheduled and unscheduled, out to 30 days post dose) will be determined. The maximum value will then be summarized by dosing group for the categories given below:

- > ULN but $\leq 1.5 \times$ ULN
- $> 1.5 \times ULN \text{ but } < 3 \times ULN$
- $\geq 3 \times ULN$
- ≥ 0.3 mg/dL increase from baseline.

Laboratory abnormalities will be graded according to CTCAE (Version 5.0, 27 November 2017). Any graded abnormality that occurs following the initiation of study drug (within 30 days post last dose) and represents at least 1-grade increase from the baseline assessment is defined as treatment emergent. A listing of all liver function test results for subjects experiencing a treatment-emergent Grade 3 or 4 liver function test will be provided.

All laboratory data will be listed.

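### The SAP's TEAE rule has no worsening clause and stops at 30 days although the safety follow-up visit may fall 31 days after last dose, so some events and laboratory values can be missing from the summary tables, though not from the listings.

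*SAP*

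**What the plan says.** **TEAE rule.** SAP Section 10 sets the TEAE rule separately for each dosing group: "AEs that started on or after the first dose of study treatment through 30 days after the last dose of study drug". It contains no clause on worsening.

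**AE collection.** The same section says that AEs and SAEs "will be collected from the time of signing of the informed consent through to the last study visit". Screening-period AEs are therefore on the database.

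**AE definition.** Protocol 13.1.1 includes a "symptom, syndrome, or illness that develops or worsens during the clinical study".

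**Laboratory rules.** SAP 10.4 calls a graded abnormality treatment-emergent if it is at least one grade above baseline and occurs after study drug starts, "within 30 days post last dose". The maximum liver-test and creatinine values are also taken only up to 30 days post dose. Protocol 14.4.5 has the same one-grade rule without an upper time limit.

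**Follow-up visit.** Protocol 11.3.6 places the safety follow-up visit "approximately 4 weeks (28 ± 3 days) after the date of their" last dose. SAP 4.1 shows the same window under Protocol Version 3.0 for those stopping early: "Safety Follow-up Visit: 28 ± 3 days after last dose of BCX9930 for subjects who discontinue BCX9930 dosing prior to the Week 52 Visit".

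**Listings.** SAP 10 and 10.4 state that every AE and every laboratory result will be listed.

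**The concern.** The SAP says the abbreviated study report will focus on safety. Two features of the TEAE rule can remove relevant events from its safety tables.

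First, an AE that begins between consent and first dose and then becomes more severe on drug has a pre-dose start date if it is kept as one record. The rule does not count it. The SAP treats worsening as treatment-emergent for laboratory values but not for AEs.

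Second, the 30-day limit is shorter than the window the protocol allows for the follow-up visit. A subject can attend on schedule and still have that visit's laboratory values excluded from the derived summaries.

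Both gaps act in one direction: they can lower the reported counts but not raise them. Elsewhere the same section is conservative, since it assigns a missing severity or relationship to the worst category.

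**Working it through.** No sample size, power or alpha bears on this point, and the plan states no figure to reproduce. The check is date arithmetic and a comparison of rules.

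**1. Follow-up window against the limit.**
- Earliest permitted day: 28 − 3 = 25 days after last dose.
- Latest permitted day: 28 + 3 = 31 days after last dose.
- SAP limit: 30 days after last dose.
- Of the seven permitted days (25 to 31), only day 31 lies beyond the limit. Here day 31 means 31 days after last dose, not Study Day 31.

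**2. The rules applied to example events.** First dose is Study Day 1. Last dose is assumed to be on Study Day 140, so the SAP limit is 140 + 30 = Study Day 170 and the window closes on 140 + 31 = Study Day 171. The onset days are assumed for illustration.

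| Example AE | SAP rule | With worsening clause, through day 31 |
|---|---|---|
| Onset in screening, no worsening | Not a TEAE | Not a TEAE |
| Onset in screening, worsens on Study Day 20, same record | Not a TEAE | TEAE |
| Same worsening entered as a new AE on Study Day 20 | TEAE | TEAE |
| Onset 25 days after last dose | TEAE | TEAE |
| Onset 29 days after last dose, found at a day-31 visit | TEAE | TEAE |
| Onset 30 days after last dose | TEAE | TEAE |
| Onset 31 days after last dose | Not a TEAE | TEAE |

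Two of the seven examples change: the worsened screening AE kept as one record, and the AE with onset on day 31.

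**3. Laboratory values.** A sample is classified by its draw date, so any value drawn on day 31 falls outside the 30-day limit. In the SAP's display list this affects Tables 14.3.2.1 (maximum liver tests) and 14.3.2.2 (maximum creatinine). It also affects treatment-emergent grading, which SAP 10.4 uses to select subjects for Listing 16.2.8.6.

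**4. Is worsening covered elsewhere?** Protocol 13.1.1 gives a recording instruction for pre-existing medical conditions that worsen. It does not say whether an AE already recorded in screening gets a new record and start date when it worsens. Protocol 13.4 has AEs followed until they resolve, which fits a single continuing record but does not settle the question.

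**5. Effect on this study.** It cannot be computed, because the documents contain no AE data. With two treated subjects, one subject wrongly left out would move an overall proportion by 1/2 = 50 percentage points, but only if that subject had no other event counted in the same row.

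**The case against.** The strongest reply is that nothing disappears from the report. All AEs and all laboratory results are listed for all subjects, and with two treated subjects a reader can see every case. This stands, and it limits the point to the summary tables and the selection of subjects for one liver-test listing.

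A second reply is that the protocol's AE definition includes worsening, so a worsened screening AE could be entered as a new AE with an on-treatment start date, which the SAP rule would count. This stands in part. The outcome depends on an eCRF convention that the documents do not state. If a new record is opened, the extra clause changes nothing; if not, the event is missed.

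A reader might also infer more than the documents support:
- *That everything found at a day-31 visit is dropped.* For AEs the rule uses onset, so an event found on day 31 that began by day 30 still counts. Only laboratory values drawn that day, and AEs with onset that day, are excluded.
- *That all five secondary safety endpoints rest on the TEAE rule.* Four do. The fifth, Grade 3 or 4 laboratory abnormalities, has its own rule in SAP 10.4, which already counts worsening but has the same 30-day limit. The SAP plans no laboratory grade table.
- *That this is the only post-treatment visit.* That is true of Version 4.0. No subject enrolled under Version 4.0, and the Version 3.0 schema in the SAP also shows a 14 ± 3 day follow-up visit for all subjects.
- *That one permitted day in seven means a 14% loss, or that 56 + 28 = 84 days of extended screening measures the risk.* The first needs visits spread evenly around a day-28 target. The second is collection time, with the extension granted case by case. Neither measures an effect on counts.

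**Conclusion.** The point holds as a minor defect in the analysis definition. The TEAE rule omits worsening after first dose, and the 30-day limit on AEs and laboratory values ends one day before the follow-up window closes. Affected events and values may be missing from the TEAE and maximum-elevation tables and from treatment-emergent grading, but they remain in the AE and laboratory listings.

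The worsening gap assumes that a worsened screening AE stays as one record with its original start date. The one-day gap needs a follow-up laboratory draw, or an AE onset, exactly 31 days after last dose. The effect on the actual counts is unknown and probably small. The documents give no basis for saying that any event has been missed or that a conclusion would change.

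**What to change.** In SAP Section 10, define a TEAE as an AE that starts, or worsens in severity, on or after first dose through the safety follow-up visit (at least 31 days after last dose). In SAP 10.4, use the same end point for the liver-test and creatinine maxima and for treatment-emergent grading.

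This takes one or two sentences and needs no new data collection. The downside is a possibly slightly higher TEAE count.
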